	(N=xx) xx (xx.x%) xx (xx.x%) xx (xx.x%) xx (xx.x%) xx (xx.x%) xx (xx.x%) xx (xx.x%) xx (xx.x%)	Placebo (N=xx) xx (xx.x%)	(N=xx) CCI (N=xx) CCI (N=xx) xx (xx.x%) xx (xx.x%) xx (xx.x%) xx (xx.x%) xx (xx.x%) xx (xx.x%)	Placebo MEDI7352 XX (XX.X%) XX (XX.X%) XX (XX.X%) XX (XX.X%) XX (XX.X%) XX (XX.X%) XX (XX.X%) XX (XX.X%)	Placebo MEDI7352 (N=xx) COIN=xx) COIN=xx) All MEDI7352 xx (xx.x%) xx (xx.x%) xx (xx.x%) xx (xx.x%) xx (xx.x%) xx (xx.x%) xx (xx.x%) xx (xx.x%)

. . .

AE = adverse event; IP = investigational product; MedDRA = Medical Dictionary for Regulatory Activities; n = number of subjects within each SOC/PT/Relatedness category; N = number of subjects per treatment group; PT = Preferred Term; SOC = System Organ Class; TEAE = treatment-emergent adverse event.

[1] Related is defined as reasonable possibility that the AE was caused by investigational product, as a ssessed by the investigator. If investigator's assessment is missing the event is judged as related.

[figure not shown]
Note: Results are n (n/N *100).

A TEAE is defined as an AE with an onset at the time of or following the start of treatment with IP.

AEs were coded using MedDRA version 26.0. Subjects are counted once for each SOC and once for each PT for the most related AE.

AEs are displayed by descending frequency of SOC, then descending frequency of PT within SOC, based on 'All MEDI7352' column. Table is sorted by international order for SOC of same frequency, and alphabetically for PT of same frequency.

Reference Listing 16.2.7.1

Programming Notes:

- SOC and PT texts should be in proper case in table.
- Present only severity categories with at least one subject.
- In case a term is not coded (e.g. in a dry run) it will be labelled as "Not Coded [SOC]" and "Not Coded [PT]", and sorted at the end of the table. SOC.
- A column for column dosing (column dosing) will only be added if Stage 4 is initiated.

Final 1 2 | 04-Oct-2023 | Page 68 of 218

[figure not shown]

Table 14.3.1.5
Treatment Emergent Adverse Events by ADA Status Category, System Organ Class and Preferred Term Safety Population

Treatment: xxxxxxx

Ticatiliciti. XXXXXXX								
	101			N. TE	TE	TE	Post-Baseline	0.1.0
G	ADA	1D1D 11	TTE ADA	Non-TE-	Persistently	Transiently	and Baseline	Only Baseline
System Organ Class	Negative	ADA Positive	TE-ADA +	ADA +	ADA +	ADA +	Positive	Positive
D C 1/T	(N=xx)	(N=xx)	(N=xx)	(N=xx)	(N=xx)	(N=xx)	(N=xx)	(N=xx)

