Preferred Term	n (n/N * 100) m	n (n/N * 100) m	n (n/N * 100) m	n (n/N * 100) m	n (n/N * 100) m	n (n/N * 100) m	n (n/N * 100) m	n (n/N * 100) m
C 1	(0()	(0()	(0/)	(0()	(0/)	(0()	(0()	(0()
Subjects with at Least	XX (XX.X%) XX	XX (XX.X%) XX	XX (XX.X%) XX	XX (XX.X%) XX	XX (XX.X%) XX	XX (XX.X%) XX	xx(xx.x%)xx	XX (XX.X%) XX
One TEAE								
System Organ Class 1	xx (xx.x%) xx	xx (xx.x%) xx	xx (xx.x%) xx	xx (xx.x%) xx	xx (xx.x%)xx	xx (xx.x%) xx	xx (xx.x%) xx	xx (xx.x%) xx
Preferred Term 1	xx (xx.x%)xx	` '					xx (xx.x%)xx	
Preferred Term 2	,	` '					xx (xx.x%) xx	
Preferred Term 3							xx(xx.x%)xx	
Tierenied Tenn 5	AA (AA.A70)AA	AA (AA.A / 0) AA	AA (AA.A.70)AA	AA (AA.A70)AA	AA (AA.A 70) AA	AA (AA.A70) AA	AA (AA.A 70) AA	AA (AA.A / 0) AA
System Organ Class 2	xx (xx x%)xx	xx (xx x%)xx	xx (xx x%)xx	xx (xx x%)xx	xx (xx x%)xx	xx (xx x%)xx	xx (xx.x%)xx	xx (xx x%)xx
Preferred Term 1	xx(xx.x%)xx				xx(xx.x%)xx		xx(xx.x%)xx	
Preferred Term 2	,	` '			xx(xx.x%)xx		xx(xx.x%)xx	
Preferred Term 3	XX (XX.X%) XX	XX (XX.X%) XX	XX (XX.X%) XX	XX (XX.X%) XX	XX (XX.X%) XX	XX (XX.X%) XX	xx(xx.x%)xx	XX (XX.X%) XX
G 4 0 C1 2	(0/)	(0/)	(0/)	(0/)	(0/)	(0/)	(0/)	(0/)
System Organ Class 3	2	, ,	,	` /	· /	` /	xx(xx.x%)xx	` /
Preferred Term 1	xx (xx.x%) xx						xx(xx.x%)xx	
Preferred Term 2		` '					xx(xx.x%)xx	
Preferred Term 3	xx(xx.x%)xx	xx(xx.x%)xx	xx(xx.x%)xx	xx(xx.x%)xx	xx(xx.x%)xx	xx(xx.x%)xx	xx(xx.x%)xx	xx(xx.x%)xx

AE = adverse event; ADA = Anti-Drug Antibodies; IP = investigational product; MedDRA = Medical Dictionary for Regulatory Activities; n = number of subjects within each SOC/PT category; N = number of subjects per ADA status category; PT = Preferred Term; SOC = System Organ Class; TE-ADA + = Treatment emergent ADA positive; TEAE = treatment-emergent adverse event.

ADA categories are defined in the Statistical Analysis Plan.

[figure not shown]
Note: Results are n (n/N *100) m is number of events.

A TEAE is defined as an AE with an onset at the time of or following the start of treatment with IP.

AEs were coded using MedDRA version 26.0. Subjects are counted once for each SOC and once for each PT.

Table is sorted by international order for SOC, and alphabetically for PT.

Reference Listing: 16.2.7.1

Programming Notes:

- SOC and PT texts should be in proper case in table.
- Repeat for Placebo. CCI and Overall.
- In case a term is not coded (e.g. in a dry run) it will be labelled as "Not Coded [SOC]" and "Not Coded [PT]", and sorted at the end of the table. SOC.

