gCV% = Geometric Coefficient of Variation (%); gMean = Geometric Mean; gSD = Geometric SD; LLOQ = Lower Limit of Quantification; n = number of subjects by treatment group at each visit for the parameter; N = number of subjects per treatment group; NC = not calculable; NQ = not quantifiable. [1] Baseline is defined as the last observation recorded prior to the first dose of treatment.

Note: serum MEDI7352 concentration units = ng/mL

Reference Listing: 16.2.10.1

Final 1 2 | 04-Oct-2023 | Page 131 of 218

Programming Notes:

- Include the following timepoints: Baseline (Day 1), Week 2, Week 4, Week 6, Week 8, Week 10: Pre-Dose, Week 10; Before End of Infusion, Week 10: 8 Hours after Infusion, Week 10 + 24 hours/ Pre-Dose, Week 11/ Pre-Dose, Week 10 + 14 Days/Pre-Dose; Week 18.
- Repeat the table for 'ADA Positive', 'ADA Negative' and 'Overall'.
- Any values reported as NRR (not reportable) or NS (missing) will be excluded from the summary tables.
- At a time point where less than or equal to 50% of the concentration values are NQ (below LLOQ), all NQ values will be set to the LLOQ, and all descriptive statistics will be calculated accordingly.
- At a time point where more than 50% (but not all) of the values are NQ, the gmean, gmean ± gSD and gCV% will be set to NC. The maximum value will be reported from the individual data, and the minimum and median will be set to NQ.
- If all concentrations are NQ at a time point, no descriptive statistics will be calculated for that time point. The gmean, minimum, median and maximum will be reported as NQ and the gCV% and gmean ± gSD as NC.

Final 1.2 | 04-Oct-2023 | Page 132 of 218

[figure not shown]

Table 14.4.2 Summary of Serum total NGF Concentrations Safety Population

ADA Status: xxxxxxxxxx

[figure not shown]
	Placebo		MEDI7352	
Visit/		CCI	CCI	CCI
Statistic	(N=xx)	(N=xx)	(N=xx)	(N=xx)
Baseline [1]				
n (n < LLOQ)	xx (xx)	xx (xx)	xx (xx)	xx(xx)
Mean (SD)	xx.x (xx.xx)	xx.x (xx.xx)	xx.x (xx.xx)	xx.x (xx.xx)
gMean $[gMean \pm gSD]$	x.xx[x.xx to x.xx]	x.xx [x.xx to x.xx]	x.xx[x.xx to x.xx]	,
gCV%	XX.X	XX.X	XX.X	XX.X
Median	XX.X, XX.X	xx.x, xx.x	XX.X, XX.X	XX.X, XX.X
Min, Max	XX, XX	XX, XX	XX, XX	xx, xx
Week 2				
n (n < LLOQ)	xx (xx)	xx (xx)	xx (xx)	xx(xx)
Mean (SD)	xx.x (xx.xx)	xx.x (xx.xx)	xx.x (xx.xx)	xx.x (xx.xx)
gMean [gMean \pm gSD]	x.xx[x.xx to x.xx]	x.xx[x.xx to x.xx]	x.xx[x.xx to x.xx]	, ,
gCV%	XX.X	XX.X	XX.X	XX.X
Median	XX.X, XX.X	XX.X, XX.X	XX.X, XX.X	XX.X, XX.X
Min, Max	XX, XX	XX, XX	XX, XX	XX, XX

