- ADA titre reported as <30 (below the minimum required dilution) is a negative result for the presence of ADA.
- Include Following timepoints: Screening, Weeks 2, 4, 8, 10, 12, 18.

Final 1 2 | 04-Oct-2023 | Page 195 of 218

Listing 16.2.10.1 Serum MEDI7352 Concentrations PK Population

			DIZ D1 1	ТКТОриг			
			PK Blood Sample				
	_	~ .	Collected? /	Date/Time of	MEDI7352		
Subject	Treatment	Study	Reason Not	Collection	Concentration		
ID	Arm	Visit	Collected	(Study Day)	(ng/mL)	Lab ID Number	Comments
					· -		
XXXXX	XXXX	XXXXXX	Yes	DDMMMYYYY/	XX	XXXXXXX	
				HH:MM(X)			
		XXXXXX	Yes	DDMMMYYYY/	XX	XXXXXXX	
				HH:MM (X)			
		XXXXXX	Yes	DDMMMYYYY/	NRR	XXXXXXX	XXXX
		700000	105	HH:MM (X)	TVICIC		70001
		XXXXXX	No /	1111.141141 (21)			
		$\mathcal{M}\mathcal{M}\mathcal{M}$					
			XXXXXX				

[figure not shown]
NA = Not Applicable; NRR = Not Reportable Result.

Note: Study Day is calculated relative to the date of first dose.

Programming Notes:

- Sort by Treatment Arm/ Subject ID / Collection Date.
- Include the following timepoints: Day 1, Week 2, Week 4, Week 6, Week 8, Week 10: Pre-Dose, Week 10; Before End of Infusion, Week 10: 8 Hours a fter Infusion, Week 10 + 24 hours: a fter Week 10/ Pre-Dose, Week 11: after Week 10/ Pre-Dose, Week 10 + 14 Days: after Week 10/ Pre-Dose, Week 18.

Final 1 2 | 04-Oct-2023 | Page 196 of 218

Listing 16.2.10.2 Serum total NGF Concentrations Safety Population

[figure not shown]
			PD Blood Sample				
Subject ID	Treatment Arm	Study Visit	Collected? / Reason Not Collected	Date/Time of Collection (Study Day)	Total NGF Concentration (pg/mL)	Lab ID Number	Comments
XXXXX	XXXX	XXXXXX	Yes	DDMMMYYYY/ HH:MM (X)	XX	XXXXXXX	
		XXXXXX	Yes	DDMMMYYYY/ HH:MM (X)	XX	XXXXXXX	
		XXXXXX	Yes	DDMMMYYYY/ HH:MM (X)	NS	XXXXXXX	XXXX
		XXXXXX	No / XXXXXX				

BLLOQ = Below the Lowest Limit of Quantitation; NA = Not Applicable; ND = Not Detected; NS = No Value due to Insufficient Volume or No Sample Received; PD: Pharmacodynamic; SAT = Greater than the Top of the Standard Curve; tNGF = total Nerve-Growth Factor. Note: Study Day is calculated relative to the date of first dose.

Programming Notes:

- Sort by Treatment Arm/ Subject ID / Collection Date.
- Include the following timepoints: Day 1, Week 2, Week 4, Week 6, Week 8, Week 10: Pre-Dose, Week 10; Before End of Infusion, Week 10: 8 Hours after Infusion, Week 10 + 24 hours, Week 11, Week 12; Week 18.

Final 1 2 | 04-Oct-2023 | Page 197 of 218

[figure not shown]

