ADA = Antidrug Antibodies; gSD = Geometric Standard Deviation; LLOQ = Lower Limit of Quantification.

Final 1 2 | 04-Oct-2023 | Page 213 of 218

PK Population = includes all subjects for who a pharmacokinetic sample was obtained and analyzed. ADA positive represents number of participants with at least one positive ADA result. ADA negative represents number of participants with only negative ADA results (no positive). Reference Listing: 16.2.10.1

Programming Notes:

- Insert the following text as upper legend: "Geometric Mean serum MEDI7352 ± Geometric Standard Deviation (Linear Scale)" for the linear plot, and "Geometric Mean serum MEDI7352 (Semi-Logarithmic Scale)" for the semi-log plot. Below legend, add legend for ADA status: "Overall", "ADA Positive", "ADA Negative".
- Insert legend with different point symbols and colors for each treatment group (CCI) for the Overall plot, and a legend with different point symbols and colors for each ADA status (ADA+, ADA-) for each treatment group plot by ADA status.
- Study Day in x axis and Serum MEDI7352 concentration (ng/mL) in y axis (in linear and log₁₀ scale, for each plot).
- Include data from the following timepoints: Baseline (Day 1), Week 2, Week 4, Week 6, Week 8, Week 10: Pre-Dose, Week 10: Before End of Infusion, Week 10: 8 Hours after Infusion, Week 10 + 24 hours, Week 11, Week 10 + 14 days, Week 18.
- Make one overall plot by treatment group, and a plot for each treatment group by ADA status for a total of 4 plots.
- Include a marker for LLOQ, and an inset within the plot with "LLOQ (1.00 ng/mL)".
- A line for column dosing (column dosing (column dosing (column)) will only be added if Stage 4 is initiated.

Final 1.2 | 04-Oct-2023 | Page 214 of 218

[figure not shown]
[figure not shown]

Figure 14.4.1.2
Pharmacokinetics: Individual Plot of Serum MEDI7352 Concentrations over time PK Population

ADA = Antidrug Antibodies; LLOQ = Lower Limit of Quantification.

[figure not shown]
PK Population = includes all subjects for who a pharmacokinetic sample was obtained and analyzed.

ADA positive represents number of participants with at least one positive ADA result.

ADA negative represents number of participants with only negative ADA results (no positive).

Reference Listing: 16.2.10.1

Final 1 2 | 04-Oct-2023 | Page 215 of 218

Programming Notes:

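### Table 14.3.1.5 counts every TEAE from first dose under one whole-study ADA label, so events before any detected ADA appear as events in treatment-emergent ADA-positive subjects

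*SAP*

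**What the plan says.** Table 14.3.1.5 (SAP shells, section 6.1), titled "Treatment Emergent Adverse Events by ADA Status Category, System Organ Class and Preferred Term Safety Population", has eight ADA columns and is repeated by treatment. Three of its notes matter here:

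- The denominator is one label per subject: "N = number of subjects per ADA status category".
- Events are taken from first dose: "A TEAE is defined as an AE with an onset at the time of or following the start of treatment with IP". Nothing in the shell conditions on onset relative to a positive sample.
- The category definitions are placed elsewhere: "ADA categories are defined in the Statistical Analysis Plan". That main text was not available for this note.

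The definitions that can be read are whole-study ones. Table 14.3.5.20 defines treatment-emergent ADA as a positive result after a negative baseline, or a four-fold or greater titre rise at any point in the study. Its note [3] restricts the denominators of the treatment-emergent rows to subjects with a baseline result and at least one post-baseline result.

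For concentrations, the footnote to Figure 14.4.1.1 reads "ADA positive represents number of participants with at least one positive ADA result", and ADA negative means no positive result. Tables 14.4.1 and 14.4.2 apply a positive/negative split at every timepoint, including the pre-dose baseline row.

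Listing 16.2.9.19 gives the sampling times: "Include Following timepoints: Screening, Weeks 2, 4, 8, 10, 12, 18".

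**The concern.** A subject's label is known only at the end of follow-up, but events are attributed to it from Day 1. If a subject has an infusion reaction on Day 1 and a first positive sample at Week 18, the table shows a TEAE in a TE-ADA+ subject. A reader would naturally take that column as the safety experience of people with antibodies.

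A second effect acts through follow-up. To be classed positive after baseline, a subject must stay long enough to be sampled after converting. The positive group is therefore selected for longer follow-up and has more time to report an event.

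The averaged drug and NGF displays share the time-ordering problem. Levels from before the first positive sample are averaged into the positive group, which would tend to dilute any loss of exposure. The size of that dilution has not been estimated.

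**Working it through.** **The plan's own figure.** The only number attached to the ADA categories is the persistence interval in Table 14.3.5.20, 16 weeks (112 days). It reproduces: 16 × 7 = 112. Among Weeks 2, 4, 8, 10, 12 and 18, only the pair Week 2 and Week 18 is that far apart. This confirms the visit grid but does not bear on the bias.

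**Inputs.** From the SAP: post-baseline ADA visits at Weeks 2, 4, 8, 10, 12 and 18; TEAEs counted from first dose; a fixed label per subject. Assumed: all subjects negative at baseline, ADA onset at constant hazard reaching 30% by Week 18, first TEAE at 0.05 per week unrelated to ADA, and 18 weeks of planned follow-up.

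**Step 1: follow-up before the first positive sample, no dropout.** The hazard is h = −ln(0.70)/18 = 0.0198 per week. The chance of first testing positive at visit v, with previous visit u, is exp(−hu) − exp(−hv):

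| Week | 2 | 4 | 8 | 10 | 12 | 18 |
|---|---|---|---|---|---|---|
| Probability | 0.0389 | 0.0373 | 0.0704 | 0.0332 | 0.0319 | 0.0884 |

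The sum is 0.300. The mean first-positive week among converters is (0.0389×2 + 0.0373×4 + 0.0704×8 + 0.0332×10 + 0.0319×12 + 0.0884×18)/0.300 = 10.3. As a share of follow-up this is 10.3/18 = 57%. At 15% and 50% incidence the same formula gives 59% and 54%.

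**Step 2: first TEAEs before the first positive sample.** The chance of a first TEAE by week t is 1 − exp(−0.05t). Weighted over the table above, the chance by the first-positive visit is 0.379. By Week 18 it is 1 − exp(−0.9) = 0.593. The ratio is 0.379/0.593 = 64%. Neither this nor Step 1 needs any dropout.

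**Step 3: fewer samples, fewer positives.** Subjects leaving at Weeks 1, 3, 5, 9 and 11 have 0, 1, 2, 3 and 4 post-baseline samples; a completer has 6. With chance p per sample, taken as independent, P(ever positive) = 1 − (1 − p)^k. At p = 0.05 this is 0.05 for one sample and 1 − 0.95^6 = 0.265 for six.

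**Step 4: spurious gap in the TEAE percentage.** This was simulated with no ADA effect and early leavers spread evenly over Weeks 0.5 to 10:

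| Dropout | Gap, ADA+ minus ADA− (points) |
|---|---|
| 0% | 0 |
| 5% | 2 |
| 10% | 4 |
| 20% | 57.6 − 50.1 = 7.5 |
| 30% | 56.5 − 45.7 = 10.8 |

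The result depends on the assumptions:

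- Spreading 20% dropout over Weeks 2 to 16 instead gives about 4 points.
- A separate model (10 to 40% ADA incidence, constant-hazard dropout of 20 to 30%, 50% TEAE risk over 18 weeks) gives 4 to 7 points.
- At 20% dropout, removing subjects with no post-baseline sample lowers 7.5 to 5.6, so that step alone does not remove the gap.
- The first-TEAE rate per subject-week at risk comes out at 0.050 in both groups, so a rate removes the follow-up part.

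**The case against.** Several stronger readings are tempting, and the documents do not support them.

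- A reader might infer that early leavers are classed negative by default. No text says so. The only stated default is for a missing baseline result. Someone positive at baseline is ADA positive, and a leaver negative at baseline but positive at the last available sample counts as persistently positive. Table 14.3.5.20 keeps subjects without a post-baseline result out of its treatment-emergent rates. What stands is that early leavers are less likely to be classed positive.
- A reader might blame the sampling schedule. Screening is sampled too, and subjects positive at baseline, including boosted ones, have no event that precedes ADA. The visit spacing only adds detection delay. The cause is the ever-positive label without an onset rule.
- A reader might extend the point to every ADA display. Figures 14.4.1.2 and 14.4.2.2 plot individual subjects, so nothing is averaged.
- A reader might say the construction alone creates the gap in TEAE percentage. It does not: with complete follow-up the gap is zero.

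Two further objections carry weight. The categories for Table 14.3.1.5 sit in SAP text not seen here, so a not-evaluable group may already exist. Even so, a fixed subject-level N combined with an all-onset TEAE definition misattributes early events unless that text adds an onset rule.

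The table is also descriptive and small. The mITT population is about 107. With, say, 24 positive and 56 negative subjects and proportions near one half, the 95% half-width of a difference is 1.96 × √(0.25/24 + 0.25/56) = 0.24, well above the artefact. This limits the harm but does not make the attribution right. Onset and sample dates can be matched by hand from the listings, but the summary table will be read first.

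**Conclusion.** The point holds for Table 14.3.1.5. As specified, it credits events before any detected ADA to subjects who convert after baseline, and it mixes ADA status with length of follow-up.

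Under the assumed 30% incidence and no ADA effect, about 57% of converters' follow-up and 64% of their first TEAEs fall before the first positive sample, with or without dropout. The gap in TEAE percentage depends wholly on dropout: 0 points with none, about 4 at 10% and 7.5 at 20%. It is smaller if dropout comes later. None of the ADA, dropout or TEAE rates is in the SAP, so these figures show the mechanism and its plausible size and are not a forecast.

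The averaged concentration displays share the time-ordering problem to an unquantified degree. No hypothesis test, error rate or sample size is affected. The change is worth making because it is cheap and the table would otherwise invite a wrong reading.

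**What to change.** In Table 14.3.1.5:

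- For subjects who become positive after baseline, show TEAEs with onset before the first positive sample separately from those on or after it.
- Add events per subject-week for each column, with the subject-weeks divided at the same date as the events.
- Require at least one post-baseline ADA result for the ADA-negative column, as note [3] of Table 14.3.5.20 does for the treatment-emergent rows, if the main SAP text does not already do so.

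In the averaged displays (Tables 14.4.1 and 14.4.2, Figures 14.4.1.1 and 14.4.2.1), add a footnote saying that ADA status is ever-positive over the study and that levels before the first positive sample are included. Classifying each level by status up to that visit is optional. It orders time correctly, but subjects then change groups between visits. The individual plots need no change.

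The cost is shell wording and some programming. No new data are needed, because event onset dates are in Listing 16.2.7.1 and ADA sample dates in Listing 16.2.9.19. The downside is smaller counts per column in a table that is already sparse.

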XXXXX/ XXXX	X	XXXXXXXXXXXXXXXXXXXXXXXXXXXXXXXXXXXXXX	DDMMMYYYY/HH:M M (X)/ DDMONYYYY/HH: MM (X)	XXXXXXXXX/ XXXXXXXXX	XXXXXXXXXX/ XXXXXXXXXX/ No	Yes	XX	XX / XXX
XXXXX/ XXXX	X	XXXXXXXXXXXXXXXXXXXXXXXXXXXXXXXXXXXXXX	DDMONYYYY/HH:M M (X)/ Ongoing	XXXXXXXXX/ XXXXXXXXX	XXXXXXXXX/ XXXXXXXXX/No	No	XX	XX / XXX

 \overline{DC} = discontinuation; ID = identification; IP = investigational product; MedDRA = Medical Dictionary for Regulatory Activities; SAE = serious adverse event; TEAE = treatment emergent adverse event.

Note: Study Day = date of interest – date of first infusion. A TEAE is defined as an adverse event with an onset at the time of or following the start of treatment with IP.

SAEs were coded using MedDRA version 26.0

^[1] Reasonable possibility AE caused by IP as assessed by the investigator.

Programming Notes:

- If time missing, display "--:--".
- AE ID number represents Record position within Subject.
- If no events meet the criteria for display (i.e, no AEs occur in the study), present "No events are reported.".
- SOC & PT text should be in proper case in table.
- Sort by Treatment ID/ Subject ID / Start Date / End Date (alphabetically for SOC if same date for two events).
- In case a term is not coded (e.g.. in a dry run) it will be labelled as "Not Coded [SOC]" and "Not Coded [PT]". SOC and PT abbreviations should be added in this case in footnote.

Final 1 2 | 04-Oct-2023 | Page 76 of 218

[figure not shown]

Table 14.3.3.2 Listing of Deaths Safety Population

[figure not shown]
Subject ID/ Treatment Arm	AE ID Number	System Organ Class/ Preferred Term/ Verbatim Term	Start Date/Time (Study Day)/ End Date/Time (Study Day)	Severity/ Relationship	Outcome/ Action Taken/ Therapy?	AE Leading to IP DC?	TEAE?	Serious? / Serious Criteria
XXXXX/ XXXX	X	XXXXXXXXXXXXXXXXXXXXXXXXXXXXXXXXXXXXXX	DDMMMYYYY/H H:MM (X)/ DDMMMYYYY/H H:MM (X)	XXXXXXXX	XXXXXXXXX/ XXXXXXXXX/ Yes	No	No	XX
XXXXX/ XXXX	X	XXXXXXXXXXXXXXXXXXXXXXXXXXXXXXXXXXXXXX	DDMMMYYYY/H H:MM (X)/ DDMMMYYYY/H:MM (X)	XXXXXXXX	XXXXXXXXX/ XXXXXXXXX/No	Yes	XX	XX / XXX
XXXXX/ XXXX	X	XXXXXXXXXXXXXXXXXXXXXXXXXXXXXXXXXXXXXX	DDMMMYYYY/H H:MM (X)/ Ongoing	H XXXXXXXX/ XXXXXXXX	XXXXXXXXX/ XXXXXXXX/ No	No	XX	XX / XXX

DC = discontinuation; ID = identification; IP = investigational product; MedDRA = Medical Dictionary for Regulatory Activities; TEAE = treatment emergent adverse event.

Note: Study Day = date of interest - date of first infusion. A TEAE is defined as an adverse event with an onset at the time of or following the start of treat ment with IP.

AEs were coded using MedDRA version 26.0

Final 1 2 | 04-Oct-2023 | Page 77 of 218

[figure not shown]

Programming Notes:

- If time missing, display "--:--".
- AE ID number represents Record position within Subject.
- If no events meet the criteria for display (i.e, no Aes occur in the study), present "No events are reported.".
- SOC & PT text should be in proper case in table.
- Sort by Treatment Arm/ Subject ID / Start Date / End Date (alphabetically for SOC if same date for two events).
- In case a term is not coded (e.g., in a dry run) it will be labelled as "Not Coded [SOC]" and "Not Coded [PT]". SOC and PT abbreviations should be added in this case in footnote.

Final 1 2 | 04-Oct-2023 | Page 78 of 218

